The data analyses will examine whether the hypothesis that there will be greater reductions in mood instability and EE in the FFT-MCC condition than in the FFT-Assess condition, and that symptomatic change will be greatest from baseline to 27 weeks in the FFT-MCC condition. Using machine-learning, we will conduct analyses of parents' speech samples to test computational

models that in preliminary studies generated proxies for parents' EE classifications (based on standard coding). We will also explore the use of adolescents' speech samples to test models for estimating **suicidal risk** and **mood instability** as measured by gold standard instruments.

SPECIFIC AIMS

The study will facilitate the translation of a technological augmentation to an evidence-based family intervention, with the goal of increasing treatment access among families with mood disorders. Our proposed strategy is to augment FFT with a mobile app called MyCoachConnect (MCC) that facilitates information exchange between clinicians and families, teaches adolescents emotion regulation skills, and enhances uptake of the communication and problem-solving skills so central to the FFT approach. We hypothesize that FFT-MCC will be more effective than FFT without MCC coaching (FFT-ASSESS) in engaging the targets of mood instability, suicidal ideation and EE and promoting improvements in adolescents' mood symptoms and quality of life over 27 weeks.

Aim #1. Standardization (Phase 1). *1a: To evaluate parents' and adolescents' subjective reactions to FFT with MCC assessments and skills coaching.*

Hypothesis 1a: After a baseline assessment, parents and HR youth will be provided with the adapted MCC app and begin the 18-week FFT protocol. Parents and adolescents will report high subjective usability and perceived utility scores for the mobile app. Based on preliminary data, we expect parents to complete > 80% and adolescents > 70% of the weekly speech samples. Parents and adolescents will report being comfortable leaving confidential information about clinical status on the HIPAA-compliant voice recorder.

Aim 1b. *To determine whether FFT providers in Phase 1 find value in weekly assessment data on the MCC portal.*

Hyp. 1b. Clinicians will report that app-based assessments are concordant with their views of family functioning and useful in treatment planning.

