Aim 2 (Phase 2): *Using in-person assessments of moods and EE at baseline, 9, 18, and 27 weeks, and MCC speech samples obtained weekly, we will determine whether targets and outcomes improve over time, and whether these improvements occur to a greater extent in FFT-MCC than in FFT-ASSESS.*

Hyp 2a. We will observe significant improvements over 27 weeks on dichotomous (high vs. low) and dimensional (number of criticisms) ratings of EE and mood instability (targets), and in the clinical outcomes of mood severity and quality of life. These improvements will be greater in FFT-MCC than in FFT-ASSESS. We predict that targets and clinical outcomes will be correlated over time, and that bigger changes in targets will be predictive of larger clinical improvements.

Hyp 2b. In both treatment conditions, we will find prognostic relationships between speech features (collected in call-ins to the voice app) and concurrent or later depression and suicide risk. We do not expect that suicide risk will change more in one MCC condition than in the other.

To more fully investigate hypothesis 2b, we will add two measures to our standard interval assessment (conducted every 9 weeks for 27 weeks) to assess suicide risk: the Suicidal Ideation Questionnaire-Junior (SIQ-Jr) (Reynolds, 1998 #1106) and the Columbia-Suicide Severity Rating Scale (Posner, 2009 #2158). We will explore both population-based training as well as within-person training to create personalized prediction models of suicide risk using

machine learning. Because we are collecting speech samples and suicide risk measures over a 6-month (27 week) period, we will be able to conduct analyses to explore the temporal dynamics of suicide risk. This includes understanding prior speech sampling as predictors of change in suicidal ideation or behaviors within and across individuals over time.

Participant eligibility (both study phases)

The **eligibility criteria** for this study are:

- (1) The family is English-speaking (although English need not be their first language);
- (2) The index adolescent is age 13 years, 0 mos. – 19 years, 11 mos.;
- (3) at least one parent has received a lifetime diagnosis of bipolar I or II disorder or major depressive disorder by the *MINI International Neuropsychiatric Interview*. The protocol does not require participation of this parent in treatment;

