Assessment results will be made available in real-time to providers in both conditions via a provider portal. Following each session (and prior to the next one), FFT providers will be able to log into the MCC web portal and review the family’s assessment results for the period up to the current session, including a graph of the adolescents’ weekly mood ratings and family functioning scores.

In the FFT-MCC condition, providers will tailor the interactive content/skills coaching based on a review of these assessments and their own observations during FFT sessions. They will select a “highlighted” module/topic for each week (e.g., communication strategies to reduce conflict over homework). When participants access the MCC mobile app, they will see this prioritized topic at the top of a list of topics and be prompted to explore the topic further within the app in between sessions. Providers’ access to participants’ adherence data will enable providers to discuss possible barriers to adherence and relevant solutions during FFT sessions. As discussed above, providers in both conditions will fill out Subjective Usability, Perceived Usefulness, and Ease of Use scales to describe their experiences of using the MCC app as an aid to therapy.

Estimation of Treatment Targets through Speech Analytics

Audio recordings of weekly speech samples provided by participants will be manually transcribed within five business day and entered into to the MCC app. An analysis script will be initiated to extract the relevant lexical features from the samples and calculate the estimated target scores to be displayed on the MCC provider portal. ***We will use machine learning algorithms to obtain weekly ratings of (1) parental EE (high vs low), (2) estimated suicidal risk scores concurrently and at later study timepoints, and (3) adolescents’ degree of mood instability based on their respective MCC speech samples.***

Speech data used in the analysis will be from audio recordings obtained when participants (youth and parents) call in to an automated voice response system and leave open-ended responses to questions reflecting on 1) how they are doing overall and 2) interactions within the family. Recordings are manually transcribed by study staff. We will utilize both lexical (primary focus of analysis) as well as acoustic features from the voice samples.

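### Hyp 2b labels as prognostic any link of speech with concurrent or later depression and suicide risk, so a same-time or unadjusted later association would count as support

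*Protocol*

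**What the plan says.** Hyp 2b (Protocol, Specific Aims, Aim 2) states, for both treatment conditions, that "we will find prognostic relationships between speech features (collected in call-ins to the voice app) and concurrent or later depression and suicide risk". The section on estimating treatment targets through speech analytics uses the same pair of timings. Among the weekly machine-learning outputs it lists "estimated suicidal risk scores concurrently and at later study timepoints".

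The paragraph after Hyp 2b is introduced as a fuller investigation of that hypothesis. It says that "we will add two measures to our standard interval assessment (conducted every 9 weeks for 27 weeks) to assess suicide risk" (the SIQ-Jr and the Columbia scale), that "we will be able to conduct analyses to explore the temporal dynamics of suicide risk", and that this extends to "understanding prior speech sampling as predictors of change in suicidal ideation or behaviors within and across individuals over time". The modelling is described as population-based and within-person machine learning.

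The Abstract gives a different emphasis: "We will also explore the use of adolescents' speech samples to test models for estimating" suicidal risk and mood instability as measured by reference instruments.

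The SAP covers PSR depression, SCARED anxiety, CGAS functioning, app engagement and skill use. It contains no speech analysis, and so no criterion for Hyp 2b. It also states that multiple comparisons were not corrected for.

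**The concern.** Three different findings could be reported under one label:

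1. Speech reflects the adolescent's present state (detection).
2. Speech is correlated with a later score (a raw lagged association).
3. Speech carries information about the later score that the present score does not (incremental prognostic value).

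Hyp 2b is met by the first alone, which is not prognosis. The second is time-ordered, but it follows almost automatically from the first when the outcome is persistent. Only the third separates forecasting from restating the current score.

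At stake is how a positive result would be read. The protocol speaks of personalized prediction models of suicide risk and plans to show speech-derived target estimates on the provider portal. A report that Hyp 2b was supported would suggest that speech forecasts suicide risk. The wording does not require any result that would show this.

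**Working it through.** **No figure to reproduce.** The documents give no sample size, power, alpha or success threshold for Hyp 2b. The SAP's one power statement concerns the group-by-visit interaction and is not an input here.

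**Reading check.**
- Hyp 2b joins concurrent and later outcomes with *or*, so either is enough.
- The lagged analysis in the next paragraph is time-ordered and refers to change. It is exploratory, names suicidal ideation or behaviors but not depression, is not made the test of Hyp 2b, and mentions no adjustment for the current score.
- The SAP adds nothing that narrows the criterion.

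**Illustration.** From the documents: N = 60 in phase 2, 1:1 allocation, so about 30 per arm. Assumed, because the documents give none:
- correlation r of a speech feature with the current score, 0.3 to 0.5;
- correlation a between scores 9 weeks apart, 0.5 to 0.7;
- two-sided alpha 0.05, one feature, one test;
- speech independent of the later score given the current score, so it has no added prognostic value.

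*Step 1, implied raw lagged correlation.* With zero partial correlation, r(speech, later) = r × a. This runs from 0.3 × 0.5 = 0.15 to 0.5 × 0.7 = 0.35.

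*Step 2, chance of significance, pooled N = 60.* Power ≈ Φ(atanh(ρ)·√(n−3) − 1.96), with √57 = 7.55.

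| Test | ρ | atanh(ρ)·√57 | Power |
|---|---|---|---|
| Concurrent | 0.30 | 2.34 | 65% |
| Concurrent | 0.50 | 4.15 | 99% |
| Later, unadjusted | 0.15 | 1.14 | 21% |
| Later, unadjusted | 0.35 | 2.76 | 79% |

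*Step 3, support required in each arm, n = 30 each.* With √27 = 5.20, square the per-arm power (independent arms, same direction).

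| Test | ρ | Power per arm | Both arms |
|---|---|---|---|
| Concurrent | 0.30 | 36% | 13% |
| Concurrent | 0.50 | 81% | 66% |
| Later, unadjusted | 0.15 | 12% | 1% |
| Later, unadjusted | 0.35 | 48% | 23% |

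*Step 4, check by simulation (5,000 runs per setting, N = 60).* With r from 0.3 to 0.5, the concurrent test was significant in about 65-99% of runs and the unadjusted later test in 22-79%. Either one was significant in about 69% (r = 0.3) to 99% (r = 0.5). The later test adjusted for the current score was significant in 4.9-5.7%, close to the nominal 5%.

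*Step 5, does a raw change score solve it?* No. For standardised scores, corr(S, Y1 − Y0) = −r·√((1 − a)/2). With r = 0.5 and a = 0.5 this is −0.5 × √0.25 = −0.25. Then atanh(0.25) × 7.55 = 1.93, and power is about 49% at N = 60, from regression to the mean alone. With r = 0.3 and a = 0.7 the correlation is −0.3 × √0.15 = −0.12 and power is about 14%.

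**The case against.** The case on the other side has real weight.

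- **Forward-looking intent.** A reader might infer that the protocol plans no prospective speech analysis. The documents do not support that. The paragraph tied to Hyp 2b names prior speech as a predictor of change, within and across individuals, and the within-person part would remove stable differences between adolescents. This stands. What remains is that the analysis is exploratory, omits depression and states no adjustment for the current score.
- **Incremental value was not promised.** An earlier measure related to a later outcome is often called prognostic without adjustment, and Hyp 2b does not say that speech outperforms a questionnaire. This stands too: gain over the current score is a recommended further standard, not a broken promise. It does not rescue the concurrent half of the hypothesis.
- **Detection is useful in itself.** A reader might infer that a suicide questionnaire from the same week would usually do as well as speech. Table 1 gives the SIQ-Jr and Columbia scale at standard intervals only, against one or two speech samples a week, so in most weeks there is no such measure. The weekly child scales listed there include the PHQ-9 and the CALS. Estimating present risk between visits is a legitimate aim.
- **The percentages do not model the plan.** The plan is machine learning, not a single-feature correlation test, and Hyp 2b refers to both conditions, which may mean support in each. This stands, and is why both readings are shown.
- **Consequences are limited.** The speech work is largely described as exploratory. The safety procedures described rest on staff and clinician review of samples and questionnaires, not on a speech-derived score.

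**Conclusion.** The point holds as one of criterion and label. Hyp 2b would be supported by a same-time association, and an unadjusted later association does not distinguish prognosis from persistence of the score. Neither the lagged exploratory analysis nor the SAP closes that gap.

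The logical argument needs no particular numbers: any feature that tracks the current score will also correlate with a later one if the score persists. The illustrative sizes rest wholly on assumed correlations, an assumed 0.05 level and a single-feature test. They vary widely with the reading of Hyp 2b. Pooled at 60 they are 65-99% concurrent and 21-79% later unadjusted; with support required in each arm of about 30 they are 13-66% and 1-23%. A reader might take the pooled figures as the trial's false-positive rate. They are not, because the documents set no such test.

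The severity is minor to moderate. It concerns an exploratory hypothesis and what may be claimed from it. It does not affect the comparison of FFT-MCC with the assessment-only condition on PSR depression, the SAP's primary outcome.

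**What to change.** Split Hyp 2b in the plan for the speech analyses.

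- **(a) Concurrent detection.** Speech against the same-interval score, kept as a legitimate exploratory aim and described as such.
- **(b) Prognosis.** Speech collected up to visit t against SIQ-Jr, C-SSRS and PSR depression at visit t+1, adjusted for the same score at visit t rather than analysed as a raw change. Report out-of-sample performance beside that of a model using the visit-t score alone. For population-trained models, keep all of a participant's data within one fold.

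Reserve *prognostic* for (b), and call the gain over the visit-t score incremental value. State whether support is judged in the pooled sample or separately in each condition.

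No new data are needed, since these outcomes are already scheduled at every standard interval. The cost is a rewording, one adjustment and one extra comparator model with its out-of-sample evaluation in 60 participants. The associations reported under (b) are likely to be smaller.

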- (3) intellectual disability (IQ < 70) from school records;
- (4) significant substance or alcohol abuse in the prior 3 months, as revealed by the MINI, resulting in a current DSM-5 substance or alcohol abuse disorder that is not in remission;
- (5) already received FFT inside or outside the context of a clinical trial;
- (6) there is current sexual or physical abuse or domestic abuse between parents or adult partners. These situations usually require notification of the Department of Child Services and forms of treatment other than FFT (e.g. trauma-focused therapy).

In cases where we exclude participants, appropriate referrals will be made (e.g., treatment for PTSD or autism) if participants are not already engaged in such treatment. We will conduct follow-up phone calls to verify treatment access or offer additional referrals.

Adolescents are not required to take any medications to be in the study, but if they (or their parents) wish, we will refer them to a child psychiatrist for medication management. If they wish, the adolescent and family may receive treatment in the Child and Adolescent Mood Disorders program (CHAMP) at UCLA without participating in the study. We will offer clinical referrals if they have no current providers. They may also continue to see their community provider. This study does not control pharmacotherapy choices or regimens, and does not cover the costs of medications or pharmacological management from a physician, as explained in the consent forms.

All relatives who are in the child's immediate milieu and are relevant to his or her care (biological or stepparents, siblings of any age, grandparents, or aunts/uncles) will be invited to take part in the family intervention sessions, regardless of their own diagnoses or treatment status.

Where will the Participants Come From?

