We are using a HIPAA-compliant, secured platform to reduce the risk of data breaches. As indicated above, there are circumstances, such as in the case of child abuse, where we will need to make a state-mandated disclosure. In the unlikely event that there is an unauthorized data breach (for example a server compromised by hackers despite best security practice implementation), participants involved as well as the UCLA IRB will be notified.

If the researchers have reasonable cause to believe that child abuse or neglect is occurring, or there are circumstances which might result in child abuse or neglect, they will comply with state laws by filing a child abuse report with the California state's Dept. of Child and Family Services. If the research staff believe that the adult or child participants are at risk of harming someone else, they are required to take necessary actions. These actions include notifying the parent of the participant's intentions, notifying others who might be affected (i.e., intended victims), or notifying the police or the Department of Child Services. In these cases, the research staff will be unable to preserve the adult's or child's confidentiality. These limits to confidentiality will be spelled out in the participants' consent and assent forms.

We will notify parents if we learn that the at-risk child is actively abusing alcohol or drugs in a way that is life-threatening or otherwise a danger to him- or herself or others. If a teen participant has experimented with a drug or alcohol on a single occasion, notifying the parents may not be indicated. Nonetheless, it will be necessary to monitor this behavior in family sessions. If we disclose these behaviors to parents, we will use extra family sessions to help resolve family conflicts and introduce preventative measures. Additional counseling sessions beyond the required number will be tabulated and included as covariates in the treatment/outcome analyses.

Privacy

All research interviews and therapy sessions will be conducted in clinical interview rooms in the Semel A-Floor CHAMP clinic or via Zoom, the HIPPA secure online platform, where the content cannot be overheard by others. CHAMP has a glassed in waiting area where participants come before their appointment. There will be no private conversations between research staff and participants in the waiting room.

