Substance or alcohol abuse. Youth who meet DSM-5 substance or alcohol abuse or dependence DSM-5 criteria will not be included. If the child shows evidence of regular substance or alcohol use after randomization (during the study protocol) and/or develops a DSM-5 substance/alcohol abuse or dependence disorder, we will retain him or her in the study protocol for as long as possible and work toward abstinence. In most cases we will make referrals for adjunctive chemical dependency treatment. We will make this determination on a case-by-case basis as medically or ethically appropriate. Study staff members will follow-up to assure that the youth and family have pursued adjunctive treatment. Adjunctive chemical dependency treatment will not preclude continued participation in the study protocol.

Participants will have been informed of these rules during the recruitment phase of the study, both through information given orally and via our informed consent procedures. We will make clear that discontinuing participation in the study will in no way jeopardize their access to other treatments at UCLA. They can have regular pharmacotherapy or psychotherapy at CHAMP or another relevant clinic even if no longer participating in the study. Whenever possible, we will continue to follow these children using the research outcome battery so that they can be included in intent-to-treat analyses.

Tolerability of the Baseline and Follow-up Assessment Batteries

Our prior experience with assessment batteries similar to the one proposed has been that they are well-tolerated by children and adults. We estimate that the initial assessment battery (MINI, YMRS, CDRS, questionnaires) will require approximately 2 – 2.5 hours from the parent and youth, which can be spread over two sessions. The follow-up interview and questionnaire battery averages -1.5 hours and will be administered at 9, 18, and 27 weeks.

The research personnel are trained to be attentive to fatigue, especially when the child is actively symptomatic. Where appropriate, the interviewer will subdivide the assessments across two or more sessions to decrease the participants' fatigue and help assure the integrity of the data. Children will be allowed to take breaks as often as they require.

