Technology Enhanced Family-Focused Treatment

Statistical Analysis Plan

Document number: NCT03913013

March 16, 2023

Date: March 16, 2023

Statistical Analysis Plan

The study hypotheses centered on the evolution from baseline to 9, 18 and 27 weeks of mean PSR depressive symptoms (primary study outcome), and secondarily, SCARED anxiety scores and CGAS functioning scores, calculated for each interval and compared across treatment conditions using linear and generalized linear mixed models (PROC MIXED and GLIMMIX, Statistical Analysis System [SAS], V 9.4). Mixed models, calculated using all available data, account for correlations induced by repeated measurements within subjects and produce unbiased estimates of missing data, assuming observations are missing at random. The models used treatment group (FFT-MCC vs. FFT-Track) and study visit (0, 9 weeks, 18 weeks, and 27 weeks) as fixed effects and participant as a random effect. Sensitivity analyses redefined mixed models to instead covary for baseline scores and to examine the effects of outliers (see online supplement).

Secondary models examined three-way interactions between treatment, study visit (baseline score and 9-, 18- and 27-week scores), and primary mood diagnoses (depressive vs. bipolar spectrum disorder) or comorbid disorders (presence/absence of ADHD or anxiety disorders) on the repeated dependent variables (depression [primary], anxiety, and global functioning [secondary]). Age, sex, parent diagnoses, and baseline parent-rated CALS mood instability scores were included as covariates. For outcomes measured at four time points in 60 study completers, we had 80% power to detect an overall group by study visit interaction corresponding to a treatment effect size of $f^2 = .03$, just above Cohen's threshold for a small effect ($f^2 = .02$). Because of the exploratory nature of the study, we did not correct for multiple comparisons.

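### Does the protocol's rule to adjust for extra counselling sessions, a count that arises after randomisation, undermine the treatment comparison?

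*Protocol*

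**What the plan says.** The rule is one sentence in the protocol section *Limits to Confidentiality*: "Additional counseling sessions beyond the required number will be tabulated and included as covariates in the treatment/outcome analyses". It closes a paragraph on telling parents about an adolescent's dangerous substance use, and the sentence before the last example of such use leads to this: "If we disclose these behaviors to parents, we will use extra family sessions to help resolve family conflicts and introduce preventative measures". The protocol requires 12 family sessions in both arms, so an additional session is one beyond those 12.

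Elsewhere the protocol mentions extra or emergency sessions for suicidality and clinical crises (*Preventing Suicidal Episodes*, *Protocol for Monitoring Safety of Speech Samples*, *Cost: Benefit Ratio*). It does not say that those sessions are covariates.

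The SAP (March 2023; the protocol is dated September 2020) fits mixed models with treatment group and visit as fixed effects and participant as a random effect. On covariates it says: "Age, sex, parent diagnoses, and baseline parent-rated CALS mood instability scores were included as covariates". On sensitivity analyses it says: "Sensitivity analyses redefined mixed models to instead covary for baseline scores and to examine the effects of outliers", and it refers to an online supplement that is not among the documents. Extra sessions appear nowhere in the SAP.

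**The concern.** The protocol sentence is worded as a commitment and names the treatment/outcome analyses. The variable is measured after randomisation and responds to how the adolescent is doing. If assignment changes the course of illness, and the course drives extra sessions, adjusting for the count removes part of the effect being estimated. If assignment changes the count by another route, adjustment can create a difference where none exists.

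The protocol also has an intent-to-treat aim: youths who stop taking part are followed where possible "so that they can be included in intent-to-treat analyses". A session-adjusted contrast need not estimate that effect. Because the SAP is silent, a reader cannot tell whether the count was left out on purpose, and someone could later present a session-adjusted result as the one the protocol called for.

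**Working it through.** **1. Is the count post-randomisation?** Yes, on either reading.
- Narrow reading: only sessions that follow disclosure of substance use. The protocol provides for this conditionally ("If the child shows evidence of regular substance or alcohol use after randomization"). Few such sessions are likely, because entry already excludes "significant substance or alcohol abuse in the prior 3 months, as revealed by the MINI" where it amounts to a current disorder not in remission.
- Wide reading: also sessions for suicidality and emergencies. This is an inference from the sentence's general wording.

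**2. Does any SAP model use it?** No. The covariate sentence sits in the paragraph on secondary moderator models, so it is unclear whether those covariates also enter the primary model. Either way, every listed covariate is a baseline characteristic.

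**3. What would the rule do to the group-by-visit term?** Let A be arm, S the adolescent's total of extra sessions and j the visit, with

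E[Y_j] = μ_j + δ_j·A + γ·S.

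Subtracting baseline gives

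E[Y_j − Y_0] = (μ_j − μ_0) + (δ_j − δ_0)·A.

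γ·S cancels, so with complete data the group-by-visit estimate does not change. Simulation gives a shift of 0.000. A running count that changes from visit to visit would matter only if sessions were dated to the visit that triggered them. Dated from the next visit, the shift is at most 0.002 SD.

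**4. What would it do to a baseline-adjusted arm contrast at week 27?** The documents give no session rates, so every input here is assumed: 30 per arm (60 at 1:1), outcome SD 1, between-visit correlation 0.5, arm effect growing linearly to its week-27 value, and Poisson sessions whose log-rate rises with symptoms at weeks 9 and 18.

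Standard error: √[(1 − 0.5²) × 2/30] = √0.05 = 0.22 SD.

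| Setting | Shift, three-visit mixed model | Shift, week-27 ANCOVA |
|---|---|---|
| True effect 0.5; wide reading (about 0.5–0.8 sessions each); slopes 0.4 / 0.7 / 1.0 | 0.009 / 0.024 / 0.045 | 0.006 / 0.014 / 0.026 |
| True effect 0.5; narrow reading (about 0.10–0.16 sessions each); same slopes | 0.002 / 0.006 / 0.010 | 0.001 / 0.005 / 0.006 |
| No effect; 35–65% more sessions in FFT-MCC at equal symptoms; wide reading | 0.028 to 0.091 | 0.017 to 0.055 |
| No effect; 65% more sessions; narrow reading; slope 0.7 | 0.021 | 0.012 |
| No effect; arm does not affect the count; slope 0.7 | under 0.002 | under 0.002 |

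In the first row the mixed-model attenuation is 0.009/0.507, 0.024/0.508 and 0.045/0.503, or about 2, 5 and 9%. The largest shift in the table is 0.091/0.22 = 0.41 of a standard error. The false-positive rate in the null settings is at most 7.0% in the mixed model (4.0–4.5% without the count) and 5.3% in the ANCOVA.

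**5. A harsher set of assumptions.** In a single-outcome model without baseline adjustment, let arm change the session rate by exp(±0.7), that is, halve or double it, with latent deterioration driving both sessions and outcome. With no true effect, adjustment moves the estimate by 0.12 SD against FFT-MCC when sessions are halved, and by 0.19 SD in its favour when they are doubled. The outcome variance in that model is 0.7² + 0.71² = 0.994, so the unadjusted standard error is √(0.994 × 2/30) = 0.26. The shift is then 0.19/0.26 = 0.73 of a standard error. If either link is missing (arm to sessions, or deterioration to sessions), there is no bias.

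**The case for a change.** The strongest case for acting is that the rule still stands on paper in a trial of 60 with no multiplicity correction, so the planned covariate set ought to be beyond doubt. An arm difference in sessions is also possible. Self-harm reports on daily or weekly questionnaires trigger clinician review, and daily ratings exist only in FFT-MCC, so that arm may have more chances of detection. Hypothesis 2a predicts greater improvement in FFT-MCC, which would lower its count if deterioration drives sessions.

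Part of this stands. The mismatch is real, and adjusting for the count would be poor practice. But the routes to an arm difference are not established: the daily items listed in Table 1 are mood, sleep, perceived criticism and stress, and on suicide risk Hypothesis 2b says: "We do not expect that suicide risk will change more in one MCC condition than in the other". The harm also requires someone to report an analysis that the SAP does not contain. The SAP keeps no record of changes from the protocol on any topic, so its silence here is not a sign of a particular lapse. Nor could a reviewer supply the missing statement, since only the sponsor knows whether the count was ever fitted and why it was left out.

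**Conclusion.** The concern does not call for a change. The protocol sentence describes an unsuitable covariate, but it is an incidental line in a confidentiality section, and the later, operative analysis document leaves the covariate out, as a careful analyst would. The interaction for which the SAP states power would be unaffected by a per-adolescent count. A baseline-adjusted contrast would shift by at most 0.09 SD under the main assumptions, or 0.19 SD in the harsher unadjusted-baseline model, in each case less than one standard error and only if arm affects the count. Those sizes rest on assumed rates, because the documents give none. The conclusion that the SAP's models omit the count rests on the text alone and is limited by the unseen online supplement. A remark on why the rule lapsed would help traceability and alter no result.
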